1.2 Rationale

1.21 Rationale for the Trial and Selected Subject Population

There is no evidence-based algorithm for the treatment of MF, but therapies have been conventionally divided into skin-directed therapy and systemic therapy. Patients with early stage disease (patch/plaque disease without nodal or visceral involvement) are treated with topical corticosteroids, topical cytostatic agents, topical retinoids, superficial radiotherapy, and phototherapy. These modalities are rarely remittive but may temporarily clear involved skin and improve pruritus.

For progressive early stage MF, high risk early-stage MF (thick plaques or follicular involvement), advanced-stage MF (presence of tumors, nodal involvement, erythroderma, visceral involvement), or SS, systemic therapy is the standard of care. Biologic response modifying agents such as IFN-alpha, bexarotene, or HDAC inhibitors are considered first line, as systemic multi-agent chemotherapy provides no survival advantage.

However, the optimal treatment sequence is unknown and there is no clear evidence that sequential or step-wise combination systemic therapy is more efficacious or contributes to long-term survival or cure. Early/initial use of pembrolizumab in the treatment of advanced MF is postulated to have a unique therapeutic synergy, whereby the direct reduction of tumor burden by pembrolizumab further enhances the baseline endogenous host anti-tumor response that is subsequently amplified with additional scheduled treatments. This rationale supports the use of pembrolizumab as initial first line systemic therapy, as the endogenous anti-tumor host response is more robust earlier in the disease course and is thus more likely to produce clinical clearance of lesional skin.

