3.0 Registration Patient Eligibility

3.1 Registration – Inclusion Criteria

3.11 Age \geq 18 years.

3.12 Histological confirmation of one of the following:

- Stage IIB-IV Mycosis Fungoides not previously treated with systemic therapy
- Stage IB/IIA Mycosis Fungoides with mSWAT \geq 20 with high risk morphologic features defined as thick plaque disease and/or follicular involvement who have failed one form of skin-directed therapy.
- Sézary Syndrome patients not previously treated with systemic therapy.

3.13 Measurable disease based on mSWAT and/or RECIST 1.1 (see Section 11.0).

3.14 Be willing to provide tissue from a newly obtained core or excisional biopsy of a tumor lesion. Note: Newly-obtained is defined as a specimen obtained up to 6 weeks (42 days) prior to registration. Exception: Subjects for whom newly-obtained samples cannot be provided (e.g. inaccessible or subject safety concern) may submit an archived specimen only upon agreement from the Sponsor.

3.15 ECOG Performance Status (PS)0 or 1 ([Appendix I](#)).

3.16 The following laboratory values obtained \leq 28 days prior to registration.

- Absolute neutrophil count (ANC) \geq 1,500 /mcL
- Platelet count \geq 100,000/mcL
- Hemoglobin \geq 9.0 g/dL or \geq 5.6 mmol/L without transfusion or EPO dependency (within 7 days of assessment)
- Serum total bilirubin \leq 1.5 X ULN OR Direct bilirubin \leq ULN for subjects with total bilirubin levels $>$ 1.5 ULN
- Aspartate transaminase (AST) and Alanine transaminase (ALT) \leq 2.5 X ULN OR \leq 5 X ULN for subjects with liver metastases
- Albumin $>$ 2.5 mg/dL
- Serum creatinine \leq 1.5 x upper limit of normal (ULN) OR Measured or calculated creatinine clearance \geq 60 ml/min for subject with creatinine levels $>$ 1.5 x institutional ULN.
- PT/INR and PTT \leq 1.5 X ULN OR if patient is receiving anticoagulant therapy and PT/INR or PTT is within therapeutic range of intended use of coagulants

3.17 Negative urine or serum pregnancy test done \leq 28 days prior to registration and \leq 72 hours prior to receiving the first dose of study medication, for women of childbearing potential only.

3.18 Female subjects of childbearing potential must be willing to use an adequate method of contraception for the course of the study through 120 days after the last dose of the study medication.

Note: Abstinence is acceptable if this is the usual lifestyle and preferred contraception for the subject

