3.2 Registration – Exclusion Criteria

3.21 Any of the following because this study involves:

an agent that has known genotoxic, mutagenic and teratogenic effects:

- Pregnant women
- Nursing women
- Men or women of childbearing potential who are unwilling to employ adequate contraception

3.22 Is currently participating and receiving study therapy or have participated in a study of an investigational agent and received study therapy or used an investigational device <= 4 weeks prior to registration.

3.23 Has a diagnosis of immunodeficiency or is receiving systemic steroid therapy or any other form of immunosuppressive therapy <= 7 days prior to registration.

3.24 Has a known history of active TB (Bacillus Tuberculosis).

3.25 Hypersensitivity to pembrolizumab or any of its excipients.

3.26 Has had a prior anti-cancer monoclonal antibody (mAb) <= 4 weeks prior to registration or who has not recovered (i.e., \leq Grade 1 or at baseline) from adverse events due to agents administered more than 4 weeks earlier.

3.27 Has had prior chemotherapy, targeted small molecule therapy, or radiation therapy <= 2 weeks prior to registration or who has not recovered (i.e., \leq Grade 1 or at baseline) from adverse events due to a previously administered agent.

- Note: Subjects with \leq Grade 2 neuropathy are an exception to this criterion and may qualify for the study.
- Note: If subject received major surgery, they must have recovered adequately from the toxicity and/or complications from the intervention prior to starting therapy.

3.28 Has a known additional malignancy that is progressing or requires active treatment. Exceptions: basal cell carcinoma of the skin or squamous cell carcinoma of the skin that has undergone potentially curative therapy or in situ cervical cancer.

3.29 Has known active central nervous system (CNS) metastases and/or carcinomatous meningitis. Exceptions: subjects with previously treated brain metastases may participate provided they are stable (without evidence of progression by imaging <= 4 weeks prior to registration and any neurologic symptoms have returned to baseline), have no evidence of new or enlarging brain

metastases, and are not using steroids for at least \leq 7 days prior to registration. This exception does not include carcinomatous meningitis which is excluded regardless of clinical stability.

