9.51 Acceptable Concomitant Medications

All treatments that the investigator considers necessary for a subject's welfare may be administered at the discretion of the investigator in keeping with the community standards of medical care. All concomitant medication will be recorded in the medical record including all prescription, over-the-counter (OTC), herbal supplements, and IV medications and fluids. If changes occur during the trial period, documentation of drug dosage, frequency, route, and date may also be included in the medical record. All concomitant medications received within 28 days before the first dose of trial treatment and 30 days after the last dose of trial treatment should be recorded. Concomitant medications

administered after 30 days after the last dose of trial treatment should be recorded for SAEs and ECIs.

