9.52 Prohibited Concomitant Medications

Subjects are prohibited from receiving the following therapies during the Screening and Treatment Phase (including retreatment of patients who develop new skin disease after achieving a complete cutaneous response) of this trial:

- Antineoplastic systemic chemotherapy or biological therapy
- Immunotherapy not specified in this protocol
- Chemotherapy not specified in this protocol
- Investigational agents other than pembrolizumab
- Radiation therapy
 - Note: Radiation therapy to a symptomatic solitary lesion or to the brain may be allowed at the investigator's discretion.
- Live vaccines within 30 days prior to the first dose of trial treatment and while participating in the trial. Examples of live vaccines include, but are not limited to, the following: measles, mumps, rubella, varicella/zoster, yellow fever, rabies, BCG, and typhoid vaccine.
- Systemic glucocorticoids for any purpose other than to modulate symptoms from an event of clinical interest of suspected immunologic etiology. The use of physiologic doses of corticosteroids may be approved after consultation with the sponsor.

Subjects who, in the assessment by the investigator, require the use of any of the aforementioned treatments for clinical management should be removed from the trial. Subjects may receive other medications that the investigator deems to be medically necessary.

The Exclusion Criteria describes other medications which are prohibited in this trial.

There are no prohibited therapies during the Post-Treatment Follow-up Phase.

9.6 a Toxicity management for immune-related AEs associated with pembrolizumab

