16.0 Statistical Considerations and Methodology

16.1 Overview

This is a phase II study designed to assess the overall cutaneous response rate at cycle 9 in MF patients treated with pembrolizumab. It is a single one-stage design with an interim analysis based on the Simon optimal design with 85% power and 10% Type I error.

NOTE: As per Amendment 4, accrual will cease after the enrollment of 10 patients due to sponsor decision on funding. Thus, the study power and type I error will not be appropriate for the analysis, as the study will not be able to go to full accrual. The study will be analyzed at the pre-defined interim step.

16.11 Endpoint:

The primary endpoint is overall cutaneous response (cutaneous complete response (CR), cutaneous 90 response (CR90) or cutaneous partial response (PR)) as defined using the mSWAT score as stated in section 11.0. Throughout Section 16.0, CR, CR90 or PR will be considered synonymous with “success”, unless specified otherwise. All patients meeting the eligibility criteria who have signed a consent form and have begun treatment will be evaluable for response.

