16.2 Statistical Design

- 16.21 Design: The largest success proportion where the proposed treatment regimen would be considered ineffective in this population is 15%, and the smallest success proportion that would warrant subsequent studies with the proposed regimen in this patient population is 35%. This design uses 28 evaluable patients to test the null hypothesis that the true complete response rate is at most 15%.
- 16.22 Interim Analysis: Enter 10 evaluable patients to the study. If there are less than 2 successes in the first 10 evaluable patients, we will consider this regimen ineffective in this patient population and terminate this study. Otherwise, if the number of successes is at least 2, we will continue accrual.
- 16.23 **N/A as per Amendment 4:** Final Decision rule: If 6 or fewer successes are observed in the first 28 evaluable patients, we will consider this regimen ineffective in this patient population. Otherwise, if the number of successes is at least 7, this will be considered evidence of promising activity and the treatment may be recommended for further testing in subsequent studies.
- 16.24 **N/A as per Amendment 4:** NOTE: We will not suspend accrual at the interim analysis to allow the first 10 patients to become evaluable, unless undue toxicity is observed. Given the limited overall sample size and the inclusion of an adverse events stopping rule, we feel it is ethical to not halt accrual for the interim analysis. However, if accrual is extremely rapid, we may temporarily suspend accrual in order to obtain safety data on these patients before re-opening accrual to further patients.

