16.4 Analysis Plan

16.41 Primary Outcome Analysis: The mSWAT score at baseline and cycle 9 will be used for change in baseline calculations. All calculated values will use the last-observation-carried forward for any participants who withdraw, are lost to follow up, or exit the study per protocol. The proportion of successes will be estimated by the number of successes divided by the total number of evaluable patients will be analysed using Mann-Whitney U for nonparametric data and the student t-test. Confidence intervals for the true success proportion will be calculated according to the approach of Duffy and Santner (Duffy D 1987).

16.42 Secondary Outcome Analysis: These analyses will include all patients meeting the eligibility criteria who have signed a consent form and have begun treatment, including patients who fail to achieve a complete or partial response.

Adverse Events: All eligible patients that have initiated treatment will be considered evaluable for assessing adverse event rate(s). The maximum grade for each type of adverse event will be recorded for each patient, and frequency tables will be reviewed to determine patterns. Additionally, the relationship of the adverse event(s) to the study treatment will be taken into consideration.

Response Rates:

Changes in mSWAT scores from baseline will be evaluated at cycle 9. Summary statistics will be calculated.

Patients will be assigned response based on the mSWAT criteria in section 11.0. Proportions of patients will be calculated and described using summary statistics. Proportions of interest are patients having CR, CR90 and PR; patients having stable subcutaneous disease; patients having progressive cutaneous disease; and patients having an overall systemic response rate.

Progression free survival time is defined for all evaluable patients as the time from registration to relapse or death due to any cause. Patients are censored if they have not achieved a progression at the time of analysis. The distribution of progression-free survival will be estimated using the method of Kaplan-Meier. In addition, the progression-free survival rate at 5 years after registration will be reported.

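### The primary analysis has no rule for radiation or skin-directed treatment given before the cycle-9 mSWAT, so a response first reached after such treatment counts as a pembrolizumab success

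*Combined protocol and SAP*

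**What the plan says.** **Endpoint.** Section 11.211 defines overall cutaneous response as a fall of at least 50% in whole-skin mSWAT, with weights of 1 for patch, 2 for plaque and 4 for tumor. It makes no provision for lesions treated by other means. Section 16.41 states: "The mSWAT score at baseline and cycle 9 will be used for change in baseline calculations". Its only handling rule is last observation carried forward for patients who withdraw, are lost or exit. Section 16.11 makes every eligible, consented patient who starts treatment evaluable.

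**Other treatment during the trial.** Section 9.52 lists radiation as prohibited, then adds: "Note: Radiation therapy to a symptomatic solitary lesion or to the brain may be allowed at the investigator's discretion". A later sentence in 9.52 says that patients who need a listed treatment should leave the trial. The steroid item covers systemic glucocorticoids only. Topical corticosteroids, topical retinoids and phototherapy do not appear. Section 9.51 says: "All treatments that the investigator considers necessary for a subject's welfare may be administered at the discretion of the investigator". Section 9.52 has a similar general permission for other medications.

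**Activity of skin-directed treatment.** Section 1.21 names topical agents, superficial radiotherapy and phototherapy as treatments for early-stage disease and says: "These modalities are rarely remittive but may temporarily clear involved skin and improve pruritus".

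**Entry.** Exclusion 3.27 reads: "Has had prior chemotherapy, targeted small molecule therapy, or radiation therapy <= 2 weeks prior to registration". No washout is given for topical agents other than through the chemotherapy item, or for phototherapy. Stage IB/IIA patients are those "who have failed one form of skin-directed therapy" (section 3.12).

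**The concern.** The trial has one arm, and its endpoint is a skin-area score that, by the protocol's own account, other treatments can move. If a patient starts or steps up a topical agent or phototherapy on MF lesions, or has a skin lesion irradiated, before the cycle-9 assessment, the resulting fall in mSWAT enters the primary analysis as a pembrolizumab effect. There is no control arm in which the same thing would happen and cancel out.

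Such use is foreseeable. Some patients arrive from skin-directed care, and section 15.17 lists rash and pruritus as very common with pembrolizumab.

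What is at stake is the one decision left. After Amendment 4 the study is analysed at the interim step, where fewer than 2 successes in 10 means that the regimen is considered ineffective (section 16.22).

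**Working it through.** **1. Inputs.** Section 16.21 sets the largest success proportion at which the regimen "would be considered ineffective in this population is 15"%. The cut-off is 2 of 10 (16.22), and 10 patients are enrolled (16.1 and 16.31).

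**2. The plan's own figures.** With success rate q,

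P(at least 2 of 10) = 1 − (1 − q)^10 − 10·q·(1 − q)^9.

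At q = 0.15 this is 1 − 0.1969 − 0.3474 = 0.456. At 0.20, 0.25, 0.30 and 0.35 it is 0.624, 0.756, 0.851 and 0.914. All five match the table in 16.33. The "Simon optimal design with 85% power and 10% Type I error" in section 16.1 also reproduces: stopping at 1 or fewer of 10 and requiring at least 7 of 28 gives an exact type I error of 0.098 and power of 0.855. No stated figure is wrong on this point.

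**3. Can another treatment move mSWAT far enough?** These are constructed cases using the section 11.211 weights.

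- Patches on 10% BSA and plaques on 5%: 10×1 + 5×2 = 20, the entry minimum for stage IB/IIA. If a topical agent clears the patches, 10 remains, a 50% fall and a response.
- One tumor of 2% BSA and patches on 6%: 2×4 + 6×1 = 14. If radiation clears the tumor, 6 remains, a 57% fall.
- In general, clearing one tumor of b% BSA gives a 50% fall on its own only if 4b is at least half of baseline, that is, if baseline mSWAT is at most 8b: 8 for 1% BSA, 16 for 2%, 24 for 3%. Stage IB/IIA patients need at least 20; section 3.12 sets no minimum for stage IIB-IV. Below that share, radiation can still top up a partial effect.

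Skin-directed treatment over larger areas is therefore the broader route, and single-lesion radiation the narrower one.

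**4. Effect of one such response.** It turns 1/10 into 2/10: 10% (exact 95% interval 0.3% to 44.5%) becomes 20% (2.5% to 55.6%), and the regimen is no longer labelled ineffective. The intervals are Clopper-Pearson, for illustration; section 16.41 names another method. Given that one spurious success has occurred, the chance of reaching the cut-off at a true 15% is the chance of at least 1 in the other nine: 1 − 0.85^9 = 1 − 0.2316 = 0.768.

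**5. Effect by frequency.** Let c be the share of true non-responders converted by other skin treatment. The documents give no value, so c is an assumption. Then q = 0.15 + 0.85c.

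| c (assumed) | q | P(at least 2 of 10) |
|---|---|---|
| 0% | 0.150 | 0.456 |
| 2% | 0.167 | 0.517 |
| 5% | 0.1925 | 0.601 |
| 10% | 0.235 | 0.720 |
| 20% | 0.320 | 0.879 |

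**6. Does another provision close the gap?**

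- Exclusion 3.33 covers therapy that may confound the results, but it is an investigator's judgement at entry.
- Section 9.5 carries forward only what the exclusion criteria specifically prohibit.
- Removal under 9.52 covers the listed treatments only.
- Sections 13.0 and 13.3 deal with patients who leave treatment for an alternative therapy, not with those who continue pembrolizumab alongside another treatment.

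None says how a permitted co-treatment is scored. Nor does the carry-forward rule require the carried mSWAT to predate the other treatment.

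**The case against.** Several stronger readings are tempting, and the documents do not support them.

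- **That the plan expressly allows skin-directed therapy.** It does not. Permission comes from omission together with the general clauses. Topical cytostatics may fall under the chemotherapy item, and the wording of 3.23 on immunosuppressive therapy could reach some agents at entry. Only the radiation exception is explicit.
- **That the bias always favours pembrolizumab.** A stable topical continued from before entry is already reflected in baseline mSWAT. Stopping a suppressive topical near entry could raise later scores and bias against activity. A 50% fall from the same therapy that a patient has already failed is also less plausible. The upward bias is clear for newly started or intensified treatment.
- **That the contamination could never be detected.** Section 9.51 requires concomitant medication to be recorded from 28 days before the first dose to 30 days after the last. The test schedule has dermatology examination and photography during treatment, and section 18.5 asks for dermatology notes supporting response. For 10 patients, exposure could largely be reconstructed. What is missing is a rule that uses it.
- **That 9.52 flatly contradicts itself on radiation.** The note can be read as an exception, with the removal sentence covering what stays prohibited. The text does not say so, and a clarification is enough.
- **That every co-treated patient should count as a failure.** This would penalise a patient who had already responded. At a true 35%, one forced failure lowers the chance of at least 2 successes from 0.914 to 0.879 (1 − 0.65^9 − 9×0.35×0.65^8), and two lower it to 0.831.

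It can also be said that little hangs on the cut-off, since section 16.1 states that power and type I error no longer apply and that accrual ends at 10. That reduces the consequence, but the ineffective label and the reported response proportion remain, and both are affected.

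**Conclusion.** The gap stands. As written, section 16.41 counts a response first reached after newly started or intensified skin treatment, or after radiation to a skin lesion, as a pembrolizumab success. With 10 patients and a cut-off of 2, one such response is enough to change the conclusion.

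At a true rate of 15%, the chance of reaching the cut-off rises from 0.456 to between 0.517 and 0.879 if 2% to 20% of non-responders are converted. A reader might take these figures, or the 0.768 in the working, as estimates of what will happen. They are not: the first range rests on an assumed frequency, and the second takes a spurious success as given. They show how sensitive the rule is, not how often contamination occurs.

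This should be fixed, and it is a cheap improvement. Which treatments to permit is a clinical matter and is not judged here.

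**What to change.** **In 16.41, add a timing rule:** for a patient who, before the cycle-9 score, starts or intensifies skin-directed therapy on MF lesions or has radiation to a skin lesion, success is judged on the last mSWAT recorded before that treatment began. A response first reached afterwards is not a success, and one already reached is judged on the pre-treatment score. Any carried-forward score should obey the same limit. Because section 11.41 collects mSWAT at the end of every 21-day cycle, a recent score will normally be available, and no lesion-level areas are needed.

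**Sensitivity analysis:** report the number of successes using all observed cycle-9 scores next to the primary count.

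**CRF:** at existing cycle visits, record the type, site and start and stop dates of skin-directed therapy and radiation, including anything ongoing or stopped in the 28 days before the first dose, a window that section 9.51 already covers.

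**In 9.52, reconcile** the radiation item, its note and the removal sentence by stating how they are to be read together.

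**Cost:** analysis wording and a short CRF item. There are no new visits, no change in sample size and no change to permitted care. The reported response rate may be slightly lower, and a true late responder who receives a co-treatment is counted conservatively; the sensitivity count shows by how much. With the rule in place c is 0 for these routes, and the 0.456 in section 16.33 again describes a true rate of 15%.
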